5.2 Data to be collected

Upon enrollment, the following variables will be recorded: age; sex; race; ethnicity; comorbidities; home medications; type of surgery; urgency of surgery (elective, urgent, or emergent); and date of surgery. The following data will be recorded postoperatively:

- Cardiopulmonary bypass (CPB) time
- Aortic cross clamp time
- Estimated blood loss intraoperatively
- Requirement for (and number of) red blood cell transfusions intraoperatively and for 7d
- Requirement for (and volume) of Cell Saver used intraoperatively
- Duration of invasive mechanical ventilation
- Myocardial injury, atrial fibrillation, ARDS, and infection/sepsis within 7d
- Physiologic and vital sign data, including heart rate, blood pressure, and urine output for 7d
- Daily lab values, including hemoglobin and serum creatinine, for 7d
- Receipt of renal replacement therapy within 7d
- Reoperation during hospitalization
- ICU and hospital length of stay
- ICU and hospital mortality

5.3 Methods for data collection

[figure not shown]
Each site will review electronic medical records and enter patient-level data into a central online database using REDCap, a secure, HIPAA-compliant, web-based application for building and managing databases. REDCap has many advanced features including multi-site access, audit trails, branching logic, and validation ranges for each variable to minimize keystroke errors. Clinical research coordinators will enter detailed data on demographics, comorbidities, vital signs, physiologic parameters (e.g., hourly urine output), laboratory measures, medications, and clinical outcomes.

5.4 Biological sample collections

Overview

We will collect blood and urine samples at five time points: preoperatively (after insertion of an arterial line [for blood] and after insertion of a Foley catheter [for urine]); at the end of CPB; on arrival to the ICU; and on postoperative days 1 and 2 (**Figure 4**). Blood will be obtained from arterial or central venous catheters, which are inserted preoperatively as part of routine clinical care. If, during the course of the study, neither an arterial nor central venous catheter remains in place (e.g., on postoperative day

2), blood will be obtained by peripheral venipuncture by a phlebotomist, in which case all efforts will be made to time the blood collection with a clinical blood draw to minimize discomfort. The total volume of blood collected will be 80mL. Blood will be collected in serum and heparinized vacutainers, since EDTA chelates iron. Urine (12cc) will be obtained from Foley catheters or from a clean catch voided sample if the Foley catheter is no longer in place.

Blood volume

The blood volumes shown in **Figure 4** represent the minimum volume required to perform the comprehensive assays for the study. Preoperatively and at the end of CPB we will collect 25mL of blood, which will allow us to isolate peripheral blood mononuclear cells (PBMCs) and store them in liquid nitrogen for immunophenotyping, including flow cytometry, RNA sequencing (RNA-Seq), and qPCR. Specifically, collection of 25mL of blood will be divided as 20mL of plasma and 5mL of serum. The 20mL of plasma will allow us to isolate approximately 20×10^6 PBMCs, since each mL of blood contains approximately 10^6 PBMCs. We will aliquot and store these 20×10^6 PBMCs into four aliquots of 5×10^6 PBMCs each. Aliquot #1 will be used for flow cytometry studies to assess monocyte expression of IL-6, TNF α , HLA-DR, TLR4, PD-L1, IL-1 β , IL-10, CD163, heme oxygenase-1, ferroportin, transferrin receptor 1, and iron uptake transporters (DMT1, ZIP14). These markers will be used to assess the effect of DFO (versus normal saline) on the inflammatory phenotype of monocytes postoperatively. Further, they will be used to assess whether the effect of DFO versus normal saline on clinical parameters (AKI and extrarenal acute organ injury) differs according to preoperative differences in monocyte expression of these markers. Aliquot #2 will be used to quantify intracellular iron concentrations using the calcein-AM method.⁸⁴ Aliquot #3 will be used for RNA-Seq of monocytes to facilitate discovery of novel transcripts influenced by DFO. Aliquot #4 will be used for qPCR to validate the targets identified by RNA-Seq.

The volume of blood drawn at the other time points will be 10mL, as shown in **Figure 4**. This will include 5mL of blood drawn into a serum vacutainer and 5mL drawn into a heparinized plasma vacutainer. The serum and plasma will be centrifuged, subaliquoted, and stored at -80°C . 5mL of blood contains approximately 2.5mL of plasma/serum (approximately 50% of whole blood is plasma/serum), which will allow us to archive eight 300 μL plasma and serum aliquots at each time point. These aliquots will be used to measure the following parameters, and for storage for future hypotheses and mechanistic pathways: catalytic iron, total iron, total iron binding capacity, ferritin, hepcidin, troponin I, and oxidative stress parameters (F[2]-isoprostane and myeloperoxidase). Finally, we will collect the buffy coat (for DNA isolation) on ICU arrival and on post-operative day (POD) 1 (**Figure 4**).

Patients with a hemoglobin level <8 g/dl are excluded (section 3.2). Additionally, if during the course of the study the patient's clinical team determines that collection of blood is unsafe for the patient (e.g., if the patient is experiencing major bleeding postoperatively) then the blood sample will not be collected until the clinical team determines that it is safe. Urine will be collected for assessment of markers of tubular injury, including NGAL and KIM-1.

Sample processing, cataloging, storing, and monitoring

We will centrifuge samples as soon as possible and no more than 6h after collection and store the plasma, serum, and urine at -80C. At two time points (preoperatively and at the end of CPB) we will also isolate PBMCs and store them in liquid nitrogen. We will use screw cap micro tubes for plasma, serum, and urine samples, each pre-labeled with a unique barcode and a printed label. Each site will catalogue the date and time of collection, processing, and storage at -80C (or in liquid nitrogen, for PBMCs) for each sample. Samples will be transported every 3-6 months from MGH and BIDMC to BWH, which will serve as the central biorepository for the study. The location of each sample will be catalogued using Freezerworks, a sophisticated biorepository management and inventory program.

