Primary Objectives and Primary Endpoint	
Primary objective: To evaluate the potential efficacy of deferoxamine in reducing the risk of postoperative AKI in patients undergoing cardiac surgery.
 
Primary endpoint: Incidence of postoperative AKI, defined as follows: urine output <0.5 ml/kg/h for 6 consecutive hours (assessed within the first 48h or until the Foley catheter is removed, whichever occurs first); an increase in serum creatinine ≥0.3 mg/dl within the first 48h; an increase in serum creatinine ≥50% in the first 7 days; or receipt of renal replacement therapy in the first 7 days.

Secondary Objectives and Corresponding Endpoints	
Secondary objectives:
 
 ▪ To evaluate the potential efficacy of deferoxamine in reducing renal tubular injury in patients undergoing cardiac surgery. ▪ To evaluate the potential efficacy of deferoxamine in reducing the risk of postoperative myocardial injury, atrial fibrillation, prolonged mechanical ventilation, and sepsis in patients undergoing cardiac surgery. 
Secondary endpoints:
 
 ▪ Urinary markers of tubular injury, NGAL and KIM-1, assessed preoperatively, at the end of CPB, on arrival to the ICU, and daily for 2 days postoperatively. ▪ Postoperative myocardial injury, atrial fibrillation, prolonged mechanical ventilation, and sepsis within 7 days following cardiac surgery.
Exploratory Objectives and Corresponding Endpoints	
Exploratory objectives: To test the effects of deferoxamine on circulating markers of iron, oxidative stress, and inflammation
 
Exploratory endpoints: Circulating markers of iron status (catalytic iron, total iron, total iron binding capacity, ferritin, and hepcidin), oxidative stress (F[2]-isoprostane and myeloperoxidase), and inflammation (monocyte phenotype), each assessed pre- and postoperatively.

Sites	Brigham and Women's Hospital (BWH) Massachusetts General Hospital (MGH) Beth Israel Deaconess Medical Center (BIDMC)
Study Duration	Estimated total study duration is 4 years
Data and Safety Monitoring Committee (DSMB)	A DSMB will convene prior to study launch and after enrollment of 10, 25, 50, and 75% of the total enrollment has taken place to review safety data and any unanticipated problems. The DSMB will make recommendations as needed. The DSMB will not perform a futility analysis or consider early study completion for efficacy.

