6.2 Statistical analysis for the primary endpoint

Hypothesis 1: DFO will reduce the incidence of postoperative AKI. We will use the χ^2 test to compare the proportion of patients in the DFO versus normal saline (placebo) group who develop the primary endpoint. We will perform sensitivity analyses to assess the composite outcome of AKI or death, since death is a competing risk for AKI. We will use logistic regression to assess for heterogeneity of therapeutic response to DFO across the following subgroups: age; sex; race (White vs. non-White); preoperative eGFR (<60 vs. ≥ 60 ml/min/1.73m 2); AKI risk score (≤ 8 vs. >8); duration of CPB (<120 vs. ≥ 120 min; <120 vs. 120-180 vs. >180 min)); intraoperative RBC transfusion; and type of surgery (elective vs. urgent/emergent).

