6.4 Secondary endpoints

Other renal endpoints (clinical)

- Effect of DFO across all stages of AKI, defined by changes in SCr according to the KDIGO criteria⁸⁵ within 7 days of cardiac surgery.
- Requirement for loop or thiazide diuretics in the setting of ≥ 2 hours of oliguria (urine output <0.5 ml/kg/h for ≥ 2 consecutive hours) within 48h of cardiac surgery.
- Incidence of Major Adverse Kidney Events,⁸⁸ defined as any of the following within 7 days following cardiac surgery: $\geq 100\%$ increase in SCr, receipt of RRT, or death.

Other renal endpoints (urinary tubular injury markers)

We will assess the effect of DFO on renal tubular injury using longitudinal measures of urine NGAL and KIM-1, each assessed pre- and postoperatively (**Figure 4**). These injury markers provide complementary data to functional markers (e.g., SCr),⁸⁹ and have been used in multiple RCTs.⁹⁰⁻⁹³ Urine NGAL and KIM-1 will be normalized to the urine creatinine to account for the influence of dilution.

Extrarenal acute organ injury

We will assess the incidence of postoperative myocardial injury, atrial fibrillation, prolonged mechanical ventilation, and sepsis. The consensus definition and anticipated incidence for each endpoint is described in **Table 5**, and each was chosen based on a strong biologic rationale (**Table 5**). Assessment of atrial fibrillation will be limited to patients who do not have it at baseline. For sepsis, we will document the suspected or confirmed source of infection: pneumonia, genitourinary, biliary, bacteremia, sternal wound infection, or other. We will also document the presence/absence of septic shock, defined as sepsis with persistent hypotension requiring vasopressors to maintain mean arterial pressure ≥ 65 mm Hg and having a serum lactate level >2 mmol/L despite adequate volume resuscitation.⁹⁴

Table 5. Secondary extrarenal endpoints

Endpoint	Definition	Incidence*	Biologic Rationale
Myocardial injury	Peak postop troponin I [†] elevation >10 times the 99 th percentile URL, assessed on POD1 and 2. ⁹⁵	15%	DFO attenuates cardiac IRI ^{67, 68} and improves myocardial contractility in animals. ⁹⁶ In a RCT in 45 adults undergoing cardiac surgery, patients treated with DFO had a higher LVEF postop compared to placebo. ⁸⁰

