AF	[‡] Confirmed on a 12-lead ECG or a rhythm strip, confirmed by a healthcare provider, or treated (either medically [e.g., amiodarone] or with electrical cardioversion). Patients with AF at baseline will be excluded.	40%	In animal models, DFO prevents CPB-associated arrhythmias. ⁶⁹ In patients with chronic iron overload from beta-thalassemia major, arrhythmias are an indication for DFO treatment intensification. ⁹⁷
Prolonged ventilation	[‡] Requirement for mechanical ventilation >24h postop.	20%	In animal models, DFO attenuates the severity of mechanical ventilation- and lipopolysaccharide-induced acute lung injury. ^{70, 71}
Sepsis	[‡] Life-threatening organ dysfunction caused by a dysregulated host response to infection (assessed within 7d postop). Organ dysfunction is defined as an acute increase in the total SOFA score ≥ 2 points consequent to the infection.	10%	DFO improves monocyte phagolysosome function in vitro. ⁹⁸ Moreover, DFO improves survival in animal models of sepsis. ^{75, 76, 99}

*Anticipated incidence based on our preliminary data and published literature. [†]Troponin I is less affected by skeletal muscle breakdown than troponin T.¹⁰⁰ [‡]Defined as per the Third International Consensus Definition (Sepsis-3).⁹⁴ Abbreviations: AF, atrial fibrillation/flutter; DFO, deferoxamine; ICH, intracerebral hemorrhage; LVEF, left ventricular ejection fraction; POD, postoperative day; URL, upper reference limit.

We will assess time to liberation from IV vasoactive medications, as well as the Vasoactive-Inotropic Score during the first 24 hours. Finally, we will assess the number of ventilator-, hospital-, and ICU-free days to day 28, as well as all-cause hospital mortality. Patients who die prior to 28 days will be assigned 0 ventilator-, hospital-, and ICU-free days.

Iron and oxidative stress markers

We will assess the effect of DFO on iron and oxidative stress markers, including catalytic iron, total iron, total iron binding capacity, ferritin, hepcidin, F(2)-isoprostane, and myeloperoxidase, each assessed pre- and postoperatively (**Figure 4**).

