6.5 Statistical analysis for secondary endpoints

Hypothesis 2: DFO will attenuate peak postoperative increases in urinary markers of tubular injury (NGAL and KIM-1) and iron and oxidative stress, and will reduce the incidence of myocardial injury, atrial fibrillation, prolonged mechanical ventilation, and sepsis. For binary variables we will use the χ^2 test to compare the proportion of patients in each group who develop the endpoint. For continuous variables we will compare baseline (preoperative)-adjusted peak postoperative levels of each marker in DFO- versus placebo-treated patients using the two sample t-test or Wilcoxon rank-sum test depending on the distribution. We will also use a Generalized Estimating Equation for repeated measures to analyze longitudinal assessments of each marker in DFO- versus placebo-treated patients. For analyses of urinary tubular injury markers, we will perform sensitivity analyses using a global rank endpoint to account for anuria as a competing risk.^{101, 102} Finally, we will evaluate a composite endpoint of any renal or extrarenal acute organ injury or hospital mortality.

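### Do the 13 preoperative monocyte markers in section 5.4 need their own effect-modification analysis in section 6?

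*Combined protocol and SAP*

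**What the plan says.** Section 5.4 lists 13 proteins to be measured on stored monocytes and gives them two uses. The first is as an outcome: "These markers will be used to assess the effect of DFO (versus normal saline) on the inflammatory phenotype of monocytes postoperatively". The second is as baseline modifiers, to "assess whether the effect of DFO versus normal saline on clinical parameters (AKI and extrarenal acute organ injury) differs according to preoperative differences" in marker expression. The Synopsis places the outcome among the exploratory endpoints, as "inflammation (monocyte phenotype), each assessed pre- and postoperatively". Mononuclear cells are stored only twice: "At two time points (preoperatively and at the end of CPB) we will also isolate PBMCs and store them in liquid nitrogen".

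Section 6.2 covers effect modification for the primary endpoint: "We will use logistic regression to assess for heterogeneity of therapeutic response to DFO across the following subgroups". Eight factors follow, from age to type of surgery, and none is a monocyte marker. Section 6.4 names the extrarenal outcomes ("We will assess the incidence of postoperative myocardial injury, atrial fibrillation, prolonged mechanical ventilation, and sepsis") and the iron and oxidative stress markers. In section 6.5, Hypothesis 2 states that "DFO will attenuate peak postoperative increases in urinary markers of tubular injury (NGAL and KIM-1) and iron and oxidative stress". Inflammation is not mentioned there. In section 6 the word monocyte occurs only in the biologic rationale for sepsis in Table 5: "DFO improves monocyte phagolysosome function in vitro".

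**The concern.** Section 5.4 commits the trial to two analyses that the statistical section does not describe. The modifier analysis is the more sensitive, because it concerns which patients benefit on the primary endpoint. Section 6.2 sets out its subgroup factors, several with cut-points, so a reader could take that list as complete and be surprised by 13 further modifiers in the report.

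The marker scale, the handling of multiplicity and the exploratory status of the modifier analysis are all unstated. A chance interaction could then be presented as a finding, or a cut-point chosen after the data are seen. Section 8.2 looks ahead to a phase 3 trial, so a false modifier might influence who is enrolled next.

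**Working it through.** **1. The plan's own figure.** Section 6.3 gives 148 per group for 50% versus 34% AKI, with 80% power and two-sided 0.05. With pooled variance and mean rate 0.42:

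n = [1.96 × √(2 × 0.42 × 0.58) + 0.842 × √(0.50 × 0.50 + 0.34 × 0.66)]² / 0.16² = 148.2, so 149 per group.

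Power at 148 per group is 79.95%. The stated size holds, and nothing about the monocyte markers enters it.

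**2. What is left open.** Setting sections 5.4 and 6 side by side:

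| Element | Where it is given |
|---|---|
| Markers | Section 5.4, 13 named |
| Outcomes | AKI (6.1) and four extrarenal endpoints (6.4, Table 5) |
| Sampling times | Section 5.4: preoperative and end of bypass |
| Phenotype comparison | Not named; the continuous-marker rule in 6.5 is applicable |
| Modifier model | Not named; 6.2 uses logistic regression for the same question |
| Marker scale, multiplicity | Not stated |

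The 6.5 rule compares baseline-adjusted peak levels between arms. With one post-baseline sample, the peak is that sample. The rule sits under secondary endpoints, but the Synopsis calls the iron and oxidative stress markers exploratory and 6.4 and 6.5 analyze them all the same. Applying the rule to monocyte markers is therefore no stretch. It contains no treatment-by-marker term, so it does not supply the modifier model.

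**3. False signals.** Assume one interaction test per marker and outcome at 0.05, and no true modification. Section 5.4 speaks of assessing, so these counts are an upper reading.

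- AKI only: 13 × 0.05 = 0.65 expected. Chance of at least one if independent: 1 − 0.95^13 = 48.7%.
- All five outcomes: 13 × 5 = 65 tests and 65 × 0.05 = 3.25 expected. Chance of at least one if independent: 1 − 0.95^65 = 96.4%. In simulation it falls to between 93% and 69% for assumed marker correlations of 0.3 to 0.7.
- The eight factors already in 6.2: 8 × 0.05 = 0.40 expected and 1 − 0.95^8 = 33.7%. Bypass duration is coded two ways, so nine tests give 1 − 0.95^9 = 37.0%.

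The listed subgroups are themselves unadjusted. The monocyte markers add to the exploratory load but do not change its nature.

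**4. Price of formal control.** Simulated with 300 patients, 50% versus 34% AKI at the mean marker value, and an assumed interaction odds ratio of 0.50 per SD on a continuous marker, power is about 80% unadjusted and 44% with Bonferroni over 13. At 0.61 per SD it is 53% and 18%.

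The value 0.50 is large. The whole hypothesized DFO effect is (0.34/0.66)/(0.50/0.50) = 0.515. An interaction of 0.50 per SD implies 0.515/0.50 = 1.03 one SD below the mean and 0.515 × 0.50 = 0.26 one SD above.

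With a median split (75 per arm in each half), and DFO rates of 34% in one half and 50% in the other against placebo at 50%, power is 29% at 0.05 and 7% at 0.05/13 = 0.0038.

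**The case for a change.** The strongest case for acting is that the wording in section 5.4 is a commitment, that nothing in section 6 contains a treatment-by-marker term, and that an explicit plan carries weight only if written before unblinding. Functional form matters. In simulation, picking the best of five cut-points for one marker raises its type I error from 5% to about 16%. A median split in place of a continuous marker lowers power from 80% to 60% at the assumed odds ratio of 0.50 per SD. A short paragraph would cost little.

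The omission stands, and so does the remark about cut-points. The rest is weaker. Sections 5.4 and 6.2 do not contradict each other, since 6.2 does not claim to be the only list of modifiers. Section 8.2 ties phase 3 to a demonstrated treatment effect, not to a modifier, and describes the inflammation measures as something to explore against clinical endpoints. No passage proposes cut-points for the monocyte markers.

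A paragraph on these 13 markers would also not close the search for responders. Section 5.5 sends a dataset for machine-learning subgroup identification, and section 5.4 lists intracellular iron, RNA sequencing and qPCR, also without analyses.

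**Conclusion.** No change follows. This is missing detail for an exploratory analysis, and competent analysts would fill it in much the same way: the 6.5 comparison at the end of bypass for phenotype, and a logistic model with a treatment-by-marker term for effect modification, reported for all 13 markers as hypothesis-generating. No stated rule gives a wrong answer. Calling the end-of-bypass sample postoperative is shorthand that section 5.4 itself resolves.

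The exposure is 0.65 expected false signals for AKI, rising to 3.25 if all five outcomes are tested. Both assume testing at 0.05, which the plan does not state. Formal false-discovery control or leaving the extrarenal outcomes untested would be a matter of preference. Bonferroni, roughly the floor for such control, takes power from about 80% to 44% even for a very large modifier. Marker correlations, interaction sizes and a usable preoperative assay in all 300 analyzable patients are assumptions that the documents do not supply. The primary test, its sample size and the main conclusion do not depend on any of this.

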5.5 Sending biosamples and data outside MGB

Sending biosamples to research collaborators outside Mass General Brigham

Pending execution of a Material Transfer Agreement, we will send blood and urine samples to the following collaborators: [name], at the Muljibhai Patel Society for Research in Nephrology (Nadiad, Gurajat, India), and [name], at the University of Toledo (Toledo, OH). The purpose of shipping these samples is for measurement of catalytic iron and other iron parameters, such as hemopexin, haptoglobin, and free hemoglobin. These measurements are quite specialized, and the collaborators listed above have unique expertise in performing these measurements. Samples will be labeled with a study ID only. No patient-level data will be shared with collaborators at the Muljibhai Patel Society for Research in Nephrology.

Sending coded data to research collaborators outside Mass General Brigham

Coded data from RNA-Sequencing of peripheral blood mononuclear cells will be shared with Drs. [name] and [name] at Boston Children's Hospital, who have expertise in bioinformatics and analysis of omics data, including transcriptomics. No protected health information will be shared with collaborators at Boston Children's Hospital. We will also send a limited dataset of randomized patients to the bioinformatics company, Telperian, a clinical innovation company that integrates machine learning with clinical trial data to identify subgroups of patients who may benefit from the intervention.

